8.1.10 Myositis Function Index (FI-2)

The FI-2 is a functional outcome developed for patients with adult polymyositis or dermatomyositis assessing muscle endurance in seven muscle groups. Each muscle group is scored as the number of correctly performed repetitions with 60 or 120 maximal number of repetitions depending on muscle group. The FI-2 is a further development of the original Functional Index (FI) and has been validated as to content and construct validity and intra- and inter-rater reliability. The FI-2 can be performed on both right and left sides requiring a maximum of 33 minutes, or just on the dominant side which takes 21 minutes. If both sides are available for a given muscle set then the scores from both sides will first be averaged so that there is only one score per muscle set for the calculations below. If only one side is available then that side will be used.

The 3 types of measures for analysis will be as follows:

- Total score based on hip flexion, shoulder flexion (R/L) and neck divided by 3.
- Total score based on all 7 muscle sets.
- Individual scores for all 7 muscle sets.

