**Table 5.1-2: Study Evaluations - Double-Blind Period (IM101611)**

Study Day a	Day 1	Day 29	Day 57	Day 85	Day 113	Day 141	Day 169	
Procedure	Randomization	Wk 4/ Mo 1	Wk 8	Wk 12/ Mo 3 b	Wk 16	Wk 20	Wk 24 / Mo 6 or DB ET c	Notes
DNA for genotyping d	X							Optional collection. See Section 5.6.1.3
Efficacy Assessments								
Physician Global Assessment	X	X	X	X	X	X	X	IMACS Core Component
Subject Global Assessment	X	X	X	X	X	X	X	IMACS Core Component
Manual Muscle Test (MMT-8)	X	X	X	X	X	X	X	IMACS Core Component
Myositis Disease Activity Assessment Tool (MDAAT)	X	X	X	X	X	X	X	IMACS Core Component
Myositis Function Index (FI-2)	X			X			X	
Myositis Damage Index	X						X	
Cutaneous Disease Activity Index (CDASI)	X			X			X	For subjects with DM
████████████████████ ████████████████████							█	████████████████████
Actigraphy data collection		X	X	X	X	X	X	
Imaging Assessments								
HRCT Chest							X	For all subjects with clinically active or relevant ILD or anti-synthetase syndrome. (See Section 5.3.7.2 ).
████████████████████							█	████████████████████

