#### Myositis Function Index (FI-2)

The FI-2 is a functional outcome developed for patients with adult polymyositis or dermatomyositis assessing muscle endurance in seven muscle groups. Each muscle group is scored as the number of correctly performed repetitions with 60 or 120 maximal number of repetitions depending on muscle group. The FI-2 is a further development of the original Functional Index (FI) and has been validated as to content and construct validity and intra- and inter-rater reliability. The FI-2 can be performed on both right and left sides requiring a maximum of 33 minutes, or just on the dominant side which takes 21 minutes

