7.5.1 Hierarchical Testing for Primary and Key Secondary Endpoints

If the test for the primary endpoint (proportion of subjects who achieved IMACS DOI at Day 169) is statistically significant at a level of 5%, then a hierarchical approach for statistical testing will be used for the secondary endpoints. Hierarchical ordering of the secondary endpoints is as follows:

- Mean change from baseline in HAQ-DI at Day 169.
- MRC total improvement score at Day 169.
- Mean change from baseline in muscle endurance using FI-2 at Day 169.
- Mean change from baseline in MDAAT, based on the extramuscular disease activity VAS, at Day 169.

P-values will be presented for each of these endpoints. However, endpoints should not be interpreted for significance if they have a rank lower than that endpoint whose null hypothesis was the first that could not be rejected. That is, the significance of endpoints should not be interpreted if they have a rank lower than that endpoint whose test was the first to be non-statistically significant (p-value > 0.05).

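### FI-2 is scored on whichever side(s) are available, with no link to the side(s) tested at baseline, so a change of tested side enters the change score

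*SAP*

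**What the plan says.** Protocol 5.4.1.2 describes two ways to run the test: "The FI-2 can be performed on both right and left sides requiring a maximum of 33 minutes, or just on the dominant side". The shorter form takes 21 minutes. SAP 8.1.10 repeats this description.

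SAP 8.1.10 then reduces the data to one score per muscle set by availability: "If both sides are available for a given muscle set then the scores from both sides will first be averaged". For the other case it says: "If only one side is available then that side will be used". On the scale it says: "Each muscle group is scored as the number of correctly performed repetitions with 60 or 120 maximal number of repetitions depending on muscle group". Three kinds of measure are built from the set scores: a three-set total ("Total score based on hip flexion, shoulder flexion (R/L) and neck divided by 3"), a seven-set total and the individual sets.

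Protocol Table 5.1-2 schedules FI-2 at Day 1, Day 85 and Day 169, with no entry about sides. SAP 7.5.1 ranks this endpoint third of four secondaries: "Mean change from baseline in muscle endurance using FI-2 at Day 169". The model in SAP 7.5.4 contains baseline FI-2 and its interaction with time, but no term for side or test mode. SAP 8.3 says only that missing FI-2 values are not imputed.

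**The concern.** A change score is meaningful when the same thing is measured twice. The availability rule has no anchor to baseline, so in effect it applies separately at each visit and to each muscle set. A two-sided mean on Day 1 can be compared with a single-side score on Day 169, or the reverse. The rule does not require the single side to be the dominant one, so one single side can also replace the other.

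The protocol applies the comparability principle elsewhere: for HRCT (5.3.7.2) it asks that the baseline scanner and method be kept at follow-up. FI-2 has no equivalent instruction.

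At stake is a ranked secondary endpoint with only two post-baseline assessments in the double-blind period. It stands ahead of MDAAT in the testing order. The same scores feed the later FI-2 analyses in SAP 11.6.2.

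**Working it through.** **Plan's own figure.** The documents give no SD, effect size or power for FI-2, so there is nothing to reproduce for this endpoint. The only power figure is for the primary endpoint: about 90% with 75 per group, 60% against 33%, two-sided 5%, continuity-corrected chi-squared test. It reproduces at 89.2% (inverting the Fleiss correction) and 90.3% (exact enumeration of the corrected test). This point does not touch it, because FI-2 is not one of the six IMACS core measures in SAP 8.1.1.

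**Inputs.** The scoring rule is from SAP 8.1.10. Let D be the dominant-side score and N the other-side score for one muscle set, with no true change between visits. The documents do not give D − N. I assume 0, 2, 6, 10 and 20 repetitions, with the mean of the two sides held at 30.

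**False change for one subject and one muscle set:**

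- Both sides, then dominant only: D − (D+N)/2 = (D−N)/2
- Both sides, then other side only: N − (D+N)/2 = −(D−N)/2
- Dominant only, then other side only: N − D = −(D−N)

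For the three-set total I assume equal asymmetry in hip and shoulder and an unpaired neck test. The shift for both sides then dominant only is 2 × [(D−N)/2] / 3 = (D−N)/3.

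| D − N | Both → dominant | Both → other | Dominant → other | Three-set total, both → dominant |
|---|---|---|---|---|
| 0 | 0 | 0 | 0 | 0 |
| 2 | +1 | −1 | −2 | +0.67 |
| 6 | +3 | −3 | −6 | +2.0 |
| 10 | +5 | −5 | −10 | +3.3 |
| 20 | +10 | −10 | −20 | +6.7 |

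This component is added to any true change; it does not replace it.

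**False difference between arms, per muscle set.** If all switches go from both sides to dominant only, and asymmetry is the same in both arms, the difference is [(D−N)/2] × (difference between arms in the proportion switching).

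| D − N | Equal switching | 10-point imbalance | 20-point | 30-point |
|---|---|---|---|---|
| 2 | 0 | 0.1 | 0.2 | 0.3 |
| 6 | 0 | 0.3 | 0.6 | 0.9 |
| 10 | 0 | 0.5 | 1.0 | 1.5 |
| 20 | 0 | 1.0 | 2.0 | 3.0 |

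**Noise when switching is equal.** If a share q switches in this way and switching is unrelated to true change, the added variance per set is q(1−q)(D−N)²/4. For q = 0.10 and D − N = 10 this is 0.10 × 0.90 × 25 = 2.25, an added SD component of 1.5 repetitions. For q = 0.20 it is 0.20 × 0.80 × 25 = 4.0, or 2 repetitions. Without an FI-2 SD these cannot be turned into a loss of power.

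**After the fix.** If only side(s) tested at both visits are used, the false component is 0 at every assumed asymmetry.

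**The case against.** The strongest reply is that nothing in the documents shows that any subject switches. The sentence on the two test forms describes the instrument; it does not tell sites to choose afresh at each visit. Protocol 5.4.1.2 requires assessors trained in the specific study assessments, and a fixed mode may be set in training material outside these documents. Protocol Appendix 3 lists symmetrical weakness as a diagnostic criterion, which argues against large side differences. Assessors are blinded, so switching should be similar in both arms. FI-2 is interpreted for significance only if the primary endpoint, HAQ-DI and MRC all succeed.

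Most of this stands, and it limits the size of the point. It does not remove the gap. The one-side rule shows that the SAP provides for single-side data, and it would mis-score any departure from a fixed mode whatever site training says.

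A reader might infer something stronger: that subjects who weaken move to the shorter test, drop their weaker side, and so have their decline hidden. The documents do not support that. They do not say who uses the shorter form or that the dominant side is the stronger, and the sign reverses if the later single side is the weaker one. Some worsening subjects also leave the main analysis. Protocol 3.1.5 requires discontinuation when a change in therapy for worsening is needed before Week 12, or when rescue fails. SAP 7.5.4 bases the main secondary analyses on on-treatment data.

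**Conclusion.** The point holds as a scoring defect of unknown but probably modest size. Where the tested side(s) differ between Day 1 and a later visit, SAP 8.1.10 builds a false component into the change score: half the side difference, or the full difference when one single side replaces the other, with either sign. This follows from the rule alone.

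The size for the trial rests on side asymmetry and switching rates, which the documents do not give; every figure in repetitions above is an assumed range. The expected effect under blinding is mainly added noise. Bias between arms arises only if switching or asymmetry differs by arm. A reader might take the per-subject shifts of up to 10 or 20 repetitions as treatment bias; they are not. The primary endpoint and its power are unaffected.

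**What to change.** Amend SAP 8.1.10 before unblinding:

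- For each muscle set, compute change only from the side(s) tested at both baseline and the post-baseline visit. If no side is common, set the change for that set to missing.
- Keep one baseline value per subject, because the SAP 7.5.4 model uses baseline FI-2 and its interaction with time. For each subject and muscle set, use the side(s) available at baseline and at all of that subject's analysed post-baseline visits. If none is common to all, use the side(s) common to baseline and Day 169.
- Tabulate side switches by arm.
- Where visits remain, tell sites to repeat the side(s) tested on Day 1. This may come too late for the double-blind period, since SAP 7.2 describes the Covid-19 case review as already done; the derivation rule does not depend on it.

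The averaging rule presupposes scores by side, so no new data should be needed. The work is a short SAP paragraph, a derivation change and one table. The price is slightly less precision, because some scores rest on one side instead of two, and a few more missing values.

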8.1.11 Cutaneous Dermatomyositis Disease Area and Severity Index (CDASI)

This tool assesses the improvement in skin disease activity in subjects with dermatomyositis. Four domains are evaluated including 1) disease activity and damage in 15 anatomic locations, 2) presence of Gottron's papules on the hands, 3) periungual changes, and 4) alopecia. A total activity score and damage score are calculated.

8.1.12 Myositis Damage Index (MDI)

This tool measures the degree of disease damage of all organ systems. It is composed of a series of organ-specific questions relating to the presence or absence of a given sign or symptom or problem to measure the extent of damage, and an overall rating of the disease damage of each system using a 10 cm visual analogue scale to measure the severity of damage.

The MDI has 3 proposed scores: an extent of damage score, a severity of damage score and an extended damage score.

The proposed scoring system for the MDI extent of damage score is the sum of all 0 or 1 scores for the 11 individual organ systems (muscle, skeletal, cutaneous, gastrointestinal, pulmonary, cardiovascular, peripheral vascular, endocrine, ocular, infection, malignancy) divided by the total possible score (range = 0–35 in children, 0–37 for adolescents and 0–38 in adults). If one or more items were not assessed, the resulting score would be divided by the maximum possible score of

the assessed items. The categories of “other damage” and “global damage” are not included in the MDI extent of damage score but are scored separately.

The proposed MDI severity of damage score is the sum of the 10 cm visual analogue scale scores for each of the 11 individual organ systems divided by the total possible score (range = 0–110). If one or more organ systems were not assessed, the resulting score would be divided by the maximum possible score of the assessed items. The categories of “other damage” and “global damage” are not included in the MDI severity score but are scored separately.

The proposed MDI extended damage score is the sum of the optional items listed in italics under the systems muscle, skeletal, gastrointestinal, pulmonary, endocrine divided by the total possible score. Each optional item is scored 0 or 1, providing a range of 0–16 for the extended damage score. If one or more items were not assessed, the resulting score would be divided by the maximum possible score assessed.

8.1.13 Myositis Response Criteria

The Myositis Response Criteria (MRC) is a novel outcome measure derived by consensus for a conjoint analysis–based continuous model using absolute percent change in the IMACS DOI core set measures. A total improvement score (range 0–100) can be determined by summing scores for each core set measure based on improvement adjusted by relative weight for each core set measure (see [APPENDIX 2](#)). A total improvement score of ≥ 20 represents minimal improvement, a score of ≥ 40 represents moderate improvement, and a score of ≥ 60 represents major improvement.

8.2 Baseline Measures

For all outcome measures, the baseline value is the last assessment taken prior to first dose of study medication. In general, this is the assessment taken on study Day 1 before the administration of study medication. For some variables that are also measured during screening, if Day 1 assessments are unavailable then the last assessments prior to Day 1 from screening assessments will be used as baseline value. When there is a missing baseline assessment in joint counts, it will not be imputed, thus, subjects are excluded from any change from baseline analysis for which they have a missing baseline value. No screening assessment will be imputed as baseline measurements for subjects who require a washout before the start of the study medication.

8.3 Missing Measurements

For listings of IMACS DOI response, imputed DOI response will be included in the listings with a flag to indicate the values were imputed; missing IMACS components will be presented as missing. For determination of IMACS DOI response, handling of missing values is addressed in [Section 8.1.9](#).

For the analysis of individual components of IMACS DOI, HAQ DI and its category scores, FI-2, Myositis Response Criteria missing values will not be imputed. Subjects with only baseline

observations will be excluded from any changes from baseline analyses. Similarly for all other efficacy, safety, and immunogenicity measures and biomarkers, missing values will not be imputed.

8.4 Missing, Unknown or Partial Dates

The BMS safety guidelines for conventions relating to the handling of missing or partial dates and the determination of appropriate default values in such cases (in particular, for concomitant medication dose start-dates and end-dates and AE onset dates) will be utilized.

8.5 Day Ranges for Analysis of Time Points

Subjects do not always adhere strictly to the visit schedule timing in the protocol. Therefore the designation of visits during the double-blind period of the study will be based on the day of evaluation relative to the trial (day of first study medication = study Day 1) rather than the nominal visit recorded in the CRF. Mutually exclusive relative day windows are defined below to provide derived visits that correspond to the post-baseline time points. If a visit falls outside of the pre-specified visit windows, then the data collected at that visit will not be assigned a derived visit but will remain in the derived data sets. Determination of baseline values is addressed in [Section 8.2](#).

Designation of visits for efficacy or laboratory assessments performed at every scheduled visit is tabulated in Table 8.5-1.

Table 8.5-1: Day Ranges for Efficacy or Laboratory Assessments During the Double-Blind Period

Visit	Target Day	Assessments
Screening	< 1	< 1
Day 1 (Baseline)	1	1**
Day 29	29	8 - 43
Day 57	57	44 - 71
Day 85 (Week 12)	85	72 - 99
Day 113	113	100 - 127
Day 141	141	128 - 155
Day 169 (Week 24)*	169	156 - 211

*Note: For subjects who continue into the open-label period of study, the upper limit of this window is the first dose day of the open-label period.

**Note: See [Section 8.2](#) for baseline measures.

Designation of visits for the ANA assessments is tabulated in [Table 8.5-2](#).

10 DOCUMENT HISTORY

Table 10-1: Document History

Version Number	Author(s)	Description
1.0	[REDACTED]	Original Issue

APPENDIX 1 RELEVANT PROTOCOL DEVIATIONS

Pre-randomization

- Myositis Activity:
 - Screening MMT-8 score of 140 or more.
 - Failure to document criteria for currently active IIM or obtain approval from adjudication committee.
 - Diagnosis of Inclusion Body Myositis.
- Medication/Procedure/Other:
 - Use of rituximab within 3 months.
 - Use of immune globulin within 6 weeks.
 - Discontinuation of prohibited medication within 2 weeks.

Post-randomization

- Medication/Procedure:
 - Use at randomization of more than 1 of the allowable immunosuppressant's drugs in the Double-Blind period.
 - Use of corticosteroids above prednisone $\geq 35\text{mg/day}$ (or prednisone equivalent) for > 3 weeks or within 2 weeks of Day 169.
 - Increase of 5 mg or more per day or initiation of more than 10 mg per day of prednisone (or prednisone equivalent) that is unrelated to management of an AE or permitted rescue therapy.
 - All prohibited medication not discontinued at least 2 weeks prior to randomization with the exception of immune globulin (3 months), rituximab (6 months) and d-penicillamine (3 months). Prohibited medication in this context refers to immunomodulatory medications for the treatment of IIM which are not included as immunosuppressant medications. The following list includes examples of specific prohibited medications:
 - ◆ Adrenal Corticotrophic Hormone (ACTH), including analogues.
 - ◆ Sirolimus.
 - ◆ Everolimus.
 - ◆ Mizoribine.
 - ◆ Tofacitinib or other JAK inhibitor.
 - All investigational or approved biologic DMARD therapies other than abatacept (including but not limited to tocilizumab, adalimumab, golimumab, certolizumab, etanercept, infliximab, anakinra, rituximab, etc.).
 - Use of any investigational drug other than study medication.
- Study conduct:
 - Subject missed more than 6 consecutive doses of study medication (abatacept or placebo) during the Double-Blind period or missed more than 4 consecutive scheduled doses of study medication (abatacept or placebo) between Day 141 and Day 169.

Covid-19 Related Deviations

- Unable to attend both Day 141 and Day 169 assessments due to travel/other restrictions.
- For missed doses due to Covid-19 the same rule to define those as a relevant protocol deviation applies as under study conduct above.

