### **3.1.2 Double-Blind Period (Day 1 - Week 24)**

During this period, approximately 150 subjects will be randomized in a 1:1 ratio to one of two parallel arms in a double-blinded manner as follows (see [Table 5.1-2](#)):

**Arm A:** Active abatacept SC (125 mg) weekly + standard treatment

**Arm B:** Placebo abatacept SC weekly + standard treatment

At the time of randomization, subjects must be on a stable background treatment (“standard treatment” see [Section 3.4.1.1](#)) for IIM. No adjustment in background treatment will be allowed during this Period. Randomization will be stratified globally by 3 stratification variables: (1) Dermatomyositis (DM) vs non-DM IIM, and (2) presence or absence of interstitial lung disease (ILD), (3) Japan vs Rest of World (ROW).

Rescue therapy will be available for subjects who meet the disease worsening criteria during the double-blind period as defined in [Section 3.1.4](#).

During this period, subjects who have clinically active or relevant interstitial lung disease (ILD) or anti-synthetase syndrome as determined by the investigator must undergo pulmonary function testing and high-resolution CT (HRCT) scan of the chest during screening (prior to Day 1) and may have repeat pulmonary function testing (PFT) and HRCT scan at Wk 24. (See [Section 5.3.6](#) and [Section 5.3.7.2](#))

Subjects who participate in the sub-study of MRI muscle (thighs) imaging will have an MRI performed during screening (prior to Day 1) and Wk 24. See [Section 5.8.2](#)

Subjects who participate in the sub-study of muscle biopsy will have a muscle biopsy performed during screening (prior to Day 1) and Wk 24. See [Section 5.8.3](#)

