- e) The subject must be on background standard treatment for IIM ([Section 3.4.1.1](#)). The standard treatments that are allowed as background treatment for IIM includes:
  - i) Corticosteroids alone ([Section 3.4.1.2](#)), *or*
  - ii) One of the following immunosuppressants: methotrexate, azathioprine, mycophenolate [any formulation of mycophenolate mofetil (MMF) or mycophenolic acid (MPA)],

- tacrolimus, or cyclosporine (combinations of these treatments are not allowed during the Double-Blind Period), *or*
- iii) A combination of corticosteroids and one of the above immunosuppressants
- If using corticosteroids for IIM, the subject must have been on corticosteroids for at least 12 weeks prior to randomization and a stable dose of corticosteroids for at least 4 weeks prior to randomization.
  - If using immunosuppressants other than azathioprine, the subject must have been on the same medication for at least 12 weeks and a stable dose for at least 4 weeks prior to randomization.
  - If using azathioprine, the subject must have been on azathioprine for at least 24 weeks with a stable dose for at least 12 weeks prior to randomization.
- f) Subject Re-enrollment: This study permits one re-enrollment of a subject that has discontinued the study as a pre-treatment failure (ie, “screen failure”, the subject has not been randomized /has not been treated) for any reason (see [Section 5.1.1](#)).

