2 STUDY DESCRIPTION

2.1 Study Design

This is a 24-week, Phase 3, randomized, double-blind, placebo-controlled, multicenter, study in subjects with active Idiopathic Inflammatory Myopathy (IIM; e.g., DM, PM, autoimmune necrotizing myopathy) on standard background treatment.

In addition to the 24-week double-blind period, the study includes:

- A 28-week open-label (OL) treatment period during which all subjects will receive SC abatacept with background treatment.
- An additional 24-week open-label of SC abatacept with continued therapy from the original OL period for subjects in Japan.
- A 3-year long-term extension of SC abatacept (156 weeks) with background treatment for all subjects except subjects in the U.S. and the Czech Republic.

The primary objective for this study is to compare the clinical efficacy of weekly abatacept in combination with standard treatment to standard treatment alone by assessing the percentage of subjects who achieve the IMACS DOI after 24 weeks of treatment versus standard treatment alone in adult subjects with active IIM.

Written informed consent must be provided by the subjects prior to undergoing any procedures during the screening phase.

Subjects who meet the study inclusion criteria enter into the 24-week Double-Blind (DB) period. During the DB period, approximately 150 subjects will be randomized in a 1:1 ratio to one of two treatment groups in a double-blinded manner as follows:

- Group A: Active Abatacept SC (125mg) weekly + standard treatment.
- Group B: Placebo Abatacept SC weekly + standard treatment.

At the time of randomization, subjects must be on a stable background treatment for IIM (“standard treatment” as defined in Section 3.4.1.1 of the protocol). No adjustment in background treatment will be allowed during the DB period.

During the 24-week DB period, subjects in either treatment group who meet the criteria for worsening (as defined in protocol Section 3.1.4) at any visit between Weeks 12 and 24 are permitted to use rescue therapy. The choice of rescue therapy is at the discretion of the investigator; however, rescue treatment may not be abatacept or a prohibited medication. Rescued subjects will remain blinded to study medication through Week 24 and will begin Open-Label (OL) abatacept treatment period after Week 24, however they will be considered not to have achieved the IMACS DOI for the purpose of the primary efficacy analysis.

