6.3 Populations for Analyses

Efficacy endpoints will be summarized according to the Intent-to-Treat (ITT) population and safety endpoints will be summarized according to the as-treated analysis population. These populations are described briefly below along with other populations.

- **Intent-to-Treat Analysis Population:**

The Intent-to-Treat (ITT) analysis Population is defined to include all subjects randomized into the study for whom Case Report Form (CRF) data indicate that at least one dose of study medication (abatacept or placebo) is administered during the double-blind period.

All subjects who are randomized but never received study medication are to be excluded. Given the blinded nature of this study, it is reasonable to assume that subjects who discontinue prior to the receipt of study medication do so for reasons unrelated to study medication. Subjects are grouped according to the treatments to which they are randomized by IXRS.

ITT analysis population is also referred to as “All Randomized and Treated Subjects”.

- **As-Treated Analysis Population:**

The As-Treated analysis population contains all subjects for whom CRF data indicate that at least one dose of study medication was administered during double-blind period.

Subjects are grouped according to the treatments to which they are randomized, except in cases where information is available, which indicates that a subject receives a different treatment for the entire course of double-blind period. In this case, the subject will be presented by the treatment they actually received.

The As-Treated analysis population will also be referred as “All Treated Subjects”.

- **Per-Protocol Analysis Population:**

The Per-Protocol analysis population is defined as a subset of the ITT analysis population which excludes subjects who have relevant protocol deviations during the double-blind study period. Relevant protocol deviations are those protocol deviations that might affect the primary efficacy endpoint of the study. A programmable list of relevant protocol deviation criteria is included in [APPENDIX 1](#).

The analysis of the primary efficacy endpoint will be repeated in the Per-Protocol analysis population. The Per-Protocol analysis population will exclude subjects with at least 1 relevant protocol deviation.

- **Open-Label Treated Analysis Population:**

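### SAP Appendix 1 has no per-protocol criterion for starting, switching or raising an allowable immunosuppressant after Day 1, and its one line on these drugs is ambiguous

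*SAP*

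**What the plan says.** The rule appears in both documents. Protocol Section 3.1.2: "No adjustment in background treatment will be allowed during this Period". SAP Section 2.1: "No adjustment in background treatment will be allowed during the DB period". Protocol Section 3.3.1, item 2(e)(ii), adds of the allowable immunosuppressants: "combinations of these treatments are not allowed during the Double-Blind Period".

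SAP Section 6.3 sets the test for relevance: "Relevant protocol deviations are those protocol deviations that might affect the primary efficacy endpoint of the study". It points to Appendix 1 for the programmable criteria and states the consequence: "The Per-Protocol analysis population will exclude subjects with at least 1 relevant protocol deviation". SAP Sections 6.3 and 7.5 repeat the primary analysis in this set without condition. Protocol Section 8.2 would have done so only if more than 10% of a treatment group had relevant deviations.

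Appendix 1 mentions the allowable immunosuppressants in one criterion, under its post-randomization heading: "Use at randomization of more than 1 of the allowable immunosuppressant's drugs in the Double-Blind period". Corticosteroids have criteria for later use, including an increase of at least 5 mg/day, or a start above 10 mg/day, of prednisone or equivalent, with exceptions for adverse-event management and permitted rescue. The prohibited-medication criterion is confined to "immunomodulatory medications for the treatment of IIM which are not included as immunosuppressant medications".

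**The concern.** A per-protocol repeat is informative only about the deviations that it removes. Protocol Section 3.1.5 lists raising, adding or changing an immunosuppressant as forms of rescue, and SAP Section 7.5.2 sets rescued subjects to non-response. The plan therefore already treats such changes as able to alter the primary endpoint. Made outside rescue, they meet the SAP's own test of relevance, yet the list does not name them. The same kind of change in corticosteroids is named, and no reason is given for the difference.

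If such subjects exist and stay in the set, agreement between the per-protocol and ITT results says nothing about this deviation.

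**Working it through.** **1. Each type of change against the Appendix 1 criteria**

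| Change after Day 1, not permitted rescue | Flagged? |
|---|---|
| Steroid increase of 5 mg/day or more, or start above 10 mg/day | Yes, unless for an adverse event |
| Second allowable immunosuppressant added to the first | Depends on the reading of the one line |
| First immunosuppressant in a subject on steroids alone | No |
| Switch from one allowable agent to another | No |
| Dose increase of an allowable immunosuppressant | No |

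The one line says both at randomization and in the Double-Blind period. Read widely, it catches concurrent use of two agents. It still does not reach the last three rows. The prohibited-medication criterion excludes these drugs by definition, and the remaining drug criteria cover biologics and investigational drugs.

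**2. Who could be a responder**

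SAP Section 7.5.2 forces non-response for stopping study drug before Week 24 or receiving rescue medication. Under Protocol Section 3.1.5, rescue applies to subjects meeting worsening criteria between Weeks 12 and 24; before Week 12, a change needed for worsening means discontinuation. The exposed group is therefore subjects who change an immunosuppressant outside rescue and stay on study drug.

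**3. Design figures, checked first**

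SAP Section 5: 75 per arm, 60% vs 33%, two-sided 5%, continuity-corrected chi-squared test, power about 90%.

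- Corrected difference: 0.27 − 1/75 = 0.2567.
- Null SE: √(2 × 0.465 × 0.535/75) = 0.0815.
- Alternative SE: √((0.60 × 0.40 + 0.33 × 0.67)/75) = 0.0784.
- Power: Φ((0.2567 − 1.96 × 0.0815)/0.0784) = 89.2%. Exact enumeration gives 90.3%.

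The stated power reproduces, so the design rates serve as the base.

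**4. Size, under assumptions**

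The number of such subjects is not in the documents. Suppose k placebo subjects become responders through such a change, none of whom would have responded otherwise. Expected responders without the change: 0.33 × 75 = 24.75.

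- Kept: (24.75 + k)/75.
- Excluded: 24.75/(75 − k), since exclusion removes them from numerator and denominator.

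| k | Placebo, kept | Placebo, excluded | Change | Difference from 60%: kept → excluded |
|---|---|---|---|---|
| 1 | 34.3% | 33.4% | 0.9 | 25.7 → 26.6 |
| 3 | 37.0% | 34.4% | 2.6 | 23.0 → 25.6 |
| 5 | 39.7% | 35.4% | 4.3 | 20.3 → 24.6 |

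The same cases on abatacept, with 0.60 × 75 = 45 responders otherwise, move that arm from (45 + k)/75 to 45/(75 − k): 61.3% to 60.8%, 64.0% to 62.5%, and 66.7% to 64.3%. Here exclusion lowers the difference, by 0.5, 1.5 and 2.4 points.

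A second assumption lets the placebo changers respond at 60% to 100% and all other placebo subjects at 33%. With 4 of 75 changers kept, the difference is 25.6 to 23.4 points; with 8 of 75, it is 24.1 to 19.9. Excluding them restores 27.

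**The case against.** The strongest reply is that the plan already handles most subjects of concern. Those who worsen are the likeliest to have treatment escalated, and they are either rescued or required to discontinue; both count as non-response. Protocol Section 3.5 also makes significant non-compliance, including with medication, a reason to stop study drug. One sensitivity analysis in SAP Section 7.5.3.1 sets everyone meeting the worsening criteria to non-response, rescued or not. SAP Section 7.5.2 counts rescue at any time in the 24 weeks, so it may also capture early escalation, though it does not say so. All of this stands and narrows the exposed group. It does not empty it: significant non-compliance is a judgement, and a change made without meeting worsening criteria has no stated classification.

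Two further points stand. Protocol Section 3.4, which holds the immunosuppressant rules, is redacted, so tolerated adjustments cannot be seen. And cases on placebo would shrink the difference, making the per-protocol result conservative.

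A reader might infer that the list checks Day 1 only, so that a second agent added at, say, Week 6 is certainly missed. The wording does not support that certainty, because the line also refers to the double-blind period. A reader might also take k/75 (1.3, 4.0 or 6.7 points for k = 1, 3, 5) as what a correction would recover. Exclusion also shrinks the denominator, so the gain is about two thirds of that.

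**Conclusion.** The gap is real and narrow. Appendix 1 does not flag a first start, switch or dose increase of an allowable immunosuppressant after Day 1, and its one line on these drugs can be read two ways. Subjects who make such a change outside permitted rescue and stay on study drug are kept per protocol whatever their response. Whether they can be responders turns on rescue coding, which the SAP leaves open. If every such change were coded as rescue, the responder consequence would vanish but the list would still not exclude them.

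The effect is about 0.9 to 4.3 points on the placebo per-protocol rate for 1 to 5 cases. This assumes that all cases are on placebo, all respond, and none would have responded otherwise. The documents support neither a count nor a direction: greater frequency in the arm doing worse is plausible but not shown.

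A reader might infer that the primary result is compromised or that the gap favours abatacept. Neither follows. The ITT analysis does not use this list, and the direction depends on which arm the cases fall in. This is a correction worth making to a supportive analysis.

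**What to change.** Before unblinding, replace the line in SAP Appendix 1 with:

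> Use of more than one allowable immunosuppressant at any time in the Double-Blind Period, or start, switch to a different agent, or dose increase of an allowable immunosuppressant after randomization, that is not permitted rescue therapy.

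Add the adverse-event exception of the corticosteroid criterion if the sponsor considers it applicable. State that a change between mycophenolate formulations is not a switch, since Protocol Section 3.3.1 lists them as one option. This programs the existing rule and sets no new clinical one.

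In SAP Section 7.5.2, state whether changes made outside the rescue criteria are classed as rescue for the non-responder rule. That statement also bears on the primary analysis, so it too must be fixed before unblinding.

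The cost is one line and its programming. SAP Section 8.4 already provides for concomitant-medication start and end dates, and Section 7.2 already requires deviations to be identified before unblinding. The downside is a slightly smaller per-protocol set and exclusion on post-randomization behaviour, which the steroid criterion already entails.
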